Candidates will be excluded from the study if ANY of the following apply:

- 1. Female participants of childbearing potential who are not on some form of birth control and do not have a confirmed negative pregnancy test at baseline
- 2. Use of Propecia or any other hair growth supplements within 12 months prior to enrollment.
- 3. Use of Rogaine or Minoxidil based products within 6 months prior to enrollment.
- 4. Participants have a previous hair transplant, cell treatment, micro needling, tattooing, or any other treatment to the scalp.
- 5. Participant is suffering from an active autoimmune disease such as lupus erythematosus (systemic and cutaneous) or alopecia areata.
- 6. Photosensitivity to visible light operating within 400 850 nm or taking medication that

increases photosensitivity.

- 7. Currently suffering from a dermatological condition in the treatment area or has a significant scar in the hair treatment area that, in the opinion of the investigator, will make hair growth difficult (such as a systemic burn, malignancy, etc.)
- 8. Participant has a sensitivity or allergy to tattoo ink.
- 9. Using any medication deemed to inhibit hair growth as determined by the physician investigator.
- 10. Employed by the sponsor, clinic site, or entity associated with the conduct of the study.
- 11. Has had radiation or chemotherapy in the last 12 months.
- 12. Have any condition or situation which, in the Investigator's opinion, puts the participant at significant risk, could confound the study results, or may interfere significantly with the participant's participation in the study.
- 13. Known prior inability to complete required study visits during treatment period;
- 14. Use of any other investigational drug, therapy, or device within the past 30 days of enrollment or concurrent participation in another research study;
- 15. Are unable to communicate or cooperate with the Investigator due to language problems, poor mental development, or impaired cerebral function;
- 16. Participants who are currently involved in any investigational drug or device trial or have been enrolled in such trials within the last 3 months.

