3.0 STUDY PROCEDURES

3.1 Enrollment Procedure

Participants will not be recruited until the appropriate governmental regulatory agencies (as applicable) and the local Institutional Review Board (IRB) or Human Research Ethics Committee (HREC) have approved the study. The Investigator or the Investigator's designee will inform all participants of the purpose of the study, expected duration, number of participants, as well as all conditions of the study to include the potential risks and benefits that may result from participation, follow-up duration, and study requirements.

The Investigator or designee will review the participant's history to determine the participant's initial eligibility for study entry. Upon determination of participant eligibility, the participant will be given the opportunity to discuss any aspect of the study, the informed consent, procedure, risks, benefits, alternative therapies, and the study requirements with the Investigator or Investigator's designee prior to signing the informed consent document.

Upon determining a participant's eligibility status, the participant will be offered the opportunity to participate in the study, and the participant's initials will be entered into the study site's screening log regardless of their decision to participate in the study or not. After the participant has signed the Informed Consent, all inclusion and exclusion criteria will be verified. If the participant meets all the inclusion and none of the exclusion criteria, the participant will then become eligible for enrollment.

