3.4 Participant Assessments

3.4.1 Screening – Visit 1

Participants will be preliminarily qualified to determine eligibility, i.e., those who meet all applicable inclusion/exclusion criteria that do not require a study related procedure to be performed. Those participants that meet the preliminary qualification and who agree to participate in the study will sign an Informed Consent. At the initial screening visit, participants will have their demographic information collected, their medical and medication history collected (including duration and severity of AGA); as well as a urine pregnancy test, for females of child bearing potential.

Demographic information will be collected as follows:

- Details including age and date of birth
- Gender
- Co-morbid conditions
- Work status
- Education level
- Smoking history

3.4.2 Baseline – Visit 2

The Baseline visit is the time remaining screening procedures will be completed, with the participant enrolled and randomised to a device, if eligible. This visit can take place up to 7 days from Visit 1, or it can be conducted the same day. Participants will have a physical examination and will then fill out a baseline Hair Specific Skindex-29 Quality of Life Questionnaire. This questionnaire is a wellestablished, three-dimensional, dermatology-specific health-related quality-of-life (HRQoL) instrument designed to evaluate the impact of androgenetic alopecia (AGA) and treatment outcome on a participant's physical, psychological, social functioning and well-being. A participant must have a Hair Specific Skindex-29 total overall score of \geq 45 at baseline to be eligible for enrollment. The Skindex-29 consists of 29 items loading on emotional (10-50), functioning (12-60) and symptom (7-35) categories with total scoring ranging from 29-145. The questions refer to the previous 4-week period, and scores are given on a 5-point scale, from 'never' to 'all the time'. Greater scores indicate poorer quality of life. The scale scores are computed by transforming responses to a 100-point scale, with higher

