scores indicating a lower level of quality of life. The overall score and individual category scores will be used to demonstrate improvement over the course of the trial. Corresponding Skindex-29 cut-off scores for severely impaired HRQL are as follows: \geq 52 points on symptoms, \geq 39 on emotions, \geq 37 on functioning, and \geq 44 on the overall score. The estimated cut-off scores can be used in clinical practice to identify patients with (very) severely impaired HRQL

The Investigator will conduct a routine physical exam and record the following:

- i. Medical Assessment will be performed and the following information recorded:
- Complete history
- Physical Exam (including vital signs)
- Previous treatments for AGA
- Co-morbid conditions and any disabilities
- Duration and severity of AGA
- Concomitant medication usage
- Pregnancy Test urine dipstick (as required)
- ii. Assessments and Procedures will be collected as follows:
 - Hair Specific Skindex-29 Quality of Life Score Questionnaire

If a participant remains eligible, the Investigator will enter the participant into the study. Eligible participants will then have photographic assessments conducted and be trained on the components and use of REVIAN/SHAM and will undergo the first treatment at the PI's office. The day of the first treatment will be considered as the date of participant enrollment.

- Global Photography Image of Two Views (superior and vertex scalp)
- Shave and Tattoo Scalp
- Hair Count Macrophotography (1cm² Area)
- Instruction and 1st REVIAN/SHAM 10 Minute Treatment
- Adverse Events

A standard macrophotography technique will be provided to all investigational sites. Please refer to the Macrophotography Technique Manual for full instructions on the proper site selection for shaving and tattooing the scalp and macrophotography.

All participating investigators will undergo training on the appropriate use of the REVIAN/SHAM device. Only investigators and co-investigators qualified by training or experience in dermatological conditions of the scalp will be selected for this clinical trial.

All participants will be seen at 8-weeks, 16-, and 26-weeks following enrollment.

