3.4.8 Unscheduled Visit: Visit within 26-weeks Follow-Up

If the participant returns for a study-related unscheduled visit within the 26-weeks follow-up the following evaluations will be performed:

- Medical treatment
- Adverse event
- Concomitant medication

The following Study Assessment Table provides an overview of activities to be performed at each study visit.

	Visit 1	Visit 2	Visit 3	Visit 4	Visit 5	Visit 6
PROCEDURES	Screening (Day -7)	Baseline (Day 0)	Phone Call (7 ±3 Days)	Week 8 ^{1,2} (56 ±5 Days)	Week 16 ^{1,2} (112 ±10 Days)	Week 26 ^{1,2} (182 ±10 Days)
Informed Consent	X	X				
Demographics	Х	Х				
Medical History	Х	Х				
Medication History	Х	Х				
Inclusion/Exclusion Criteria	Х	Х				
Pregnancy Test (As required)	Х	Х				
Physical Examination		Х				Х
Instruction on Device and 1st Application		Х				
Shave and Tattoo Scalp		Х		X ³	X ³	X ³
Hair Count - Macrophotography (1cm ² Area)		Х		X	Х	Х
Global Assessment Photography (superior and vertex scalp)		Х		X	Х	Х
Growth Assessment and Questionnaires:				-		
(1) Subjective Scalp Hair Growth (SSHG) score ⁴				X	Х	Х
(2) Physician's Global Assessment (sPGA) score ⁴				X	Х	Х
(3) Hair Specific Skindex-29 QoL Questionnaire		Х		X	Х	Х
Blinded Review of Global Photographs (iPGA) ⁴				Х	Х	Х
Follow-up on Compliance and Use of REVIAN/SHAM		Х	X	X	Х	Х
Concomitant Medications		Х	Х	X	Х	Х
Adverse Events		Х	Х	X	Х	Х
End of Study / Termination / Return Device						Х

¹All visit dates are in reference to Baseline, i.e., Visit 4 occurs approximately eight weeks (56 days) after the Baseline Visit.

² Participants will continue treatments throughout the 26-weeks with a daily 10-minute treatment for a total of 56 treatments over 8 weeks, 112 treatments over 16-weeks, and 182 treatments over 26-weeks.

³ Participants may have tattoo ink reapplied to original site of ink dot application at these time periods. ⁴ SSHG, *sPGA* and *iPGA* are not taken at baseline. These assessments are conducted at the follow-up visits only.

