7.0 RISK ANALYSIS

7.1 Potential Risks

There are always risks associated with any medical device and to the medical procedure used to treat a disease. The risks associated with the use of the REVIAN System are minimal because of the unique design and use of low-risk electronic components in the system, including LEDs and low voltage battery. In comparison to other medical devices that use Helmets, Caps or Wand Devices for the treatment of alopecia, the risk to the participant using the REVIAN System is extremely low or negligible. The risk of retinal or thermal damage due to laser exposure is not present with REVIAN. The LEDs are non-coherent (radiating in all directions) and divergent as compared to devices using laser diodes. It is expected that the risks and complication rates strictly associated with the procedure using REVIAN would be like other products that are currently used in the home setting to treat alopecia. In addition, as compared to using Minoxidil (Rogaine) or Finasteride (Propecia) REVIAN has no systemic adverse effects like current pharmaceutical agents, especially in women of child-bearing potential.

In addition to the safety profile discussed above the only other additional risk with REVIAN are the fabric and plastic materials used in the inner construction of the cap, however materials are medical grade. In rare circumstances, the fabric or continued use may cause allergies, irritation, tissue reactions, allergic reactions or inflammation that may result in discomfort; or the REVIAN may fail to improve symptoms.

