An incident where the Investigator or site personnel did not conduct the study according to the investigational plan, protocol or the Investigator agreement.

Major deviation: Any deviation from participant inclusion and exclusion criteria or participant informed consent procedures.

Minor deviation: Deviation from a protocol requirement such as incomplete/inadequate participant testing procedures, non-compliance with medication regimens, follow-ups performed outside specified time windows, etc.

SERIOUS ADVERSE EVENT

A **Serious Adverse Event** (SAE) is any AE that 1) leads to death, 2) leads to serious deterioration in health resulting in a life-threatening illness or injury, 3) results in permanent impairment of a body structure or a body function, 4) requires in-patient hospitalization or prolongs existing hospitalization, 5) results in medical or surgical intervention to prevent permanent impairment to body structure or a body function, or 6) leads to fetal distress, fetal death or a congenital abnormality or birth defect.

Note:

A device malfunction may or may not result in an AE. If a device malfunctions in a manner that causes an adverse event (AE) or a serious adverse event (SAE) as defined above, then the consequence of the malfunction will be reported as an AE or SAE, as appropriate. However, all device malfunctions will also be tabulated separately, regardless of whether an adverse event results from the malfunction. Any surgical interventions for device malfunctions will also be reported as subsequent surgical interventions.

SOFT TISSUE IRRITATION

Superficial Tissue Irritation An inflammatory condition of superficial layers of the skin as a result of an aseptic irritant, such as skin reaction to suture or dressings.

Periprosthetic Soft Tissue Irritation An inflammatory condition of the tissues about the implant resulting from aseptic tissue irritation. Fluid may accumulate in the periprosthetic tissues possibly resulting in the tissue swelling, localized tenderness, pain and/or joint motion is restriction.

UNANTICIPATED ADVERSE DEVICE EFFECT (UADE)

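### As worded, exclusion criterion 1 does not keep out a woman on birth control whose baseline pregnancy test is positive or missing

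*Combined protocol and SAP*

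**What the plan says.** Exclusion 1 in protocol section 2.6 applies to women of childbearing potential "who are not on some form of birth control and do not have a confirmed negative pregnancy test at baseline". The lead-in to the list says that any single item is enough to exclude.

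Section 3.1 makes the list decisive: "If the participant meets all the inclusion and none of the exclusion criteria, the participant will then become eligible for enrollment".

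Testing is described in three places:

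- Section 3.4.1 (Screening) collects history "as well as a urine pregnancy test, for females of child bearing potential", with no exemption for contraceptive users.
- Section 3.4.2 (Baseline) lists a urine dipstick, as required, in the medical assessment. It then continues: "If a participant remains eligible, the Investigator will enter the participant into the study".
- The Study Assessment Table in section 3.4.8 marks the pregnancy test at Visits 1 and 2, again only as required.

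None of the three says what follows from a positive result.

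**The concern.** A participant-protection criterion should give the right answer when a site applies it literally. Here a single *who* governs both conditions and *and* joins them, so the item applies only to a woman who uses no contraception **and** lacks a confirmed negative test. Read that way, a contraceptive user with a positive test passes exclusion 1.

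Two things follow. First, enrolling her breaches no numbered criterion. It would therefore not meet the Appendix A definition of a major deviation, "Any deviation from participant inclusion and exclusion criteria or participant informed consent procedures", and deviation reporting would not flag it on that ground. Second, the wording does not settle whether contraception is required at all, so up to four sites could apply the item differently.

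Exclusion 1 is also the only explicit pregnancy safeguard in the documents supplied. The assessment table shows no test after Visit 2 during 26 weeks of daily use, and section 3.5 has no withdrawal rule for pregnancy. Appendix A nevertheless counts fetal distress, fetal death and birth defects among serious adverse events, so pregnancy outcomes are treated as relevant.

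**Working it through.** The plan gives no figure to reproduce here. The check is a truth table on the wording of exclusion 1, followed by a search for any other rule that closes the gap.

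**Truth table.** For a woman of childbearing potential, let B = on birth control and N = confirmed negative test at baseline.

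- As written: exclude if (not B) and (not N).
- Test-only rule: exclude if (not N).
- *Or* rule: exclude if (not B) or (not N).

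| Birth control | Confirmed negative test | As written | Test-only | *Or* |
|---|---|---|---|---|
| Yes | Yes | admitted | admitted | admitted |
| Yes | No (positive or missing) | **admitted** | excluded | excluded |
| No | Yes | admitted | admitted | excluded |
| No | No (positive or missing) | excluded | excluded | excluded |
| Combinations excluded | | 1 of 4 | 2 of 4 | 3 of 4 |

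The second row is the gap: it is admitted as written and excluded under either alternative. The third row is open. Whether a woman with a negative test and no contraception should enter depends on what the sponsor intends.

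**Does another rule close the gap?**

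- *Lead-in to the exclusion list.* It joins the numbered items with *or*. It does not separate the two conditions inside item 1.
- *Inclusion criteria 1 to 16 and exclusions 2 to 16.* None names pregnancy or contraception.
- *Exclusion 12.* It could be used, but it depends on the investigator's opinion and does not mention pregnancy.
- *Sections 3.4.1 and 3.4.2.* The test is listed ahead of the sentence on remaining eligible. Eligibility, however, is defined by the section 2.6 list through section 3.1, and that list gives the result no effect for a contraceptive user.
- *Appendix A.* A test not done would count as a minor deviation, as an inadequate testing procedure. A positive test in a contraceptive user who is then enrolled is not covered.

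**Size.** The documents do not state how many participants are women of childbearing potential. The protocol summary and section 7.3 plan about 80 women among 200, and 80/200 = 40%. That is a ceiling, because enrolment runs to age 65.

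**The case against.** The strongest reply is that the sponsor's intent is not stated, so calling the second row an error presumes it. Contraception or a negative test may have been thought sufficient. The baseline test is only as required, and section 7.1 argues that "REVIAN has no systemic adverse effects like current pharmaceutical agents, especially in women of child-bearing potential". On that reading a *missing* test in a contraceptive user is a weak concern. This has some force for a missing test, but none for a positive one: no plausible intent schedules a pregnancy test and then admits a woman who is positive because she reports contraception.

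Second, exclusion 12 covers any condition that the investigator judges to be a significant risk, a confounder or an interference with participation. Once that judgement is made, exclusion is mandatory. This stands as a practical backstop, and most investigators would probably use it. It remains discretionary, and the protocol's own description of minimal device risk makes a finding of significant risk less automatic.

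Third, SAP section 9.2 has its own closed list of major deviations (age window, deleterious concomitant medication, compliance below 80%, tattoo location) and treats everything else as minor. Correcting exclusion 1 would therefore change the Appendix A classification but not the SAP's per-protocol population. That is correct, and it confirms that this is not an analysis issue.

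Fourth, counting combinations says nothing about how often each occurs, and the consent form was not available and may carry a pregnancy rule. Both points stand. Neither supplies an eligibility rule in the protocol that bars a woman with a positive test.

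**Conclusion.** The concern holds. Taken literally, exclusion 1 excludes one of the four combinations and admits a contraceptive user whose baseline test is positive or missing. No other numbered criterion names pregnancy, and the scheduled test has no stated consequence for her.

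The practical impact is limited. The test is scheduled before first treatment, exclusion 12 is available, described device risk is low, and few women are likely to be affected. There is no effect on power, alpha or the analysis.

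The conclusion rests on the wording of the protocol alone and on one assumption, that a positive test was meant to exclude. It does not assume that contraception was meant to be mandatory. The correction should be made because the criterion protects participants and costs almost nothing to repair.

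**What to change.** Replace exclusion 1 with separate items:

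- **1a.** Exclude any woman of childbearing potential who does not have a confirmed negative pregnancy test at baseline, regardless of contraceptive use.
- **1b (only if the sponsor intends contraception to be mandatory during the 26 weeks).** Exclude any woman of childbearing potential who is not on birth control.

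Item 1a alone closes the gap. Items 1a and 1b together are equivalent to replacing *and* with *or* in the present wording. Whether to add 1b is the sponsor's decision.

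The cost is a one-line protocol clarification. The test is already marked at Visits 1 and 2, so no procedure or visit is added and sample size and analysis do not change.

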2.7 Study Duration

It is anticipated that the enrollment of participants will take approximately 7-months. All participants included in this clinical investigation will return for follow-up visits at 8-, 16- and 26-weeks post-baseline visit. Evaluation of the primary efficacy and safety endpoints will be completed on all participants at the 16-weeks post-baseline period and secondary efficacy and safety endpoints will be completed at 26-weeks post-baseline.

3.0 STUDY PROCEDURES

3.1 Enrollment Procedure

Participants will not be recruited until the appropriate governmental regulatory agencies (as applicable) and the local Institutional Review Board (IRB) or Human Research Ethics Committee (HREC) have approved the study. The Investigator or the Investigator's designee will inform all participants of the purpose of the study, expected duration, number of participants, as well as all conditions of the study to include the potential risks and benefits that may result from participation, follow-up duration, and study requirements.

The Investigator or designee will review the participant's history to determine the participant's initial eligibility for study entry. Upon determination of participant eligibility, the participant will be given the opportunity to discuss any aspect of the study, the informed consent, procedure, risks, benefits, alternative therapies, and the study requirements with the Investigator or Investigator's designee prior to signing the informed consent document.

Upon determining a participant's eligibility status, the participant will be offered the opportunity to participate in the study, and the participant's initials will be entered into the study site's screening log regardless of their decision to participate in the study or not. After the participant has signed the Informed Consent, all inclusion and exclusion criteria will be verified. If the participant meets all the inclusion and none of the exclusion criteria, the participant will then become eligible for enrollment.

3.2 Process for Obtaining Informed Consent

The patients will be informed by the Investigator or Investigator's designee that they are free to refuse participation in this research study. If they elect to participate, it will be made clear that they may withdraw from the study at any time without prejudicing further care.

The Investigator or the Investigator's designee will inform participants that their medical records will be subject to review by the sponsor or appropriate regulatory bodies. This information will be used during the analysis of the results of the clinical study, but the participants' identities will be treated as confidential. Participants will be assigned a unique study participant code that will not reveal the participants' identity. This code will be used on all data and data collection forms during the study period.

The Investigator will explain the conditions of the study, giving the participant sufficient time to ask questions and to consider whether to participate. Eligible participants who agree to participate will be asked to sign and date an IRB/HREC approved informed consent form (ICF). One copy of the ICF shall be returned to the Investigator and filed in the participant's case history; the other copy is for the participant to keep.

